## **Prior and Concomitant Medications and Therapies**

All medications and therapies being taken/used by the subject at the time of consent or at any time during the study will be recorded. All medications and therapies for alopecia areata, will be recorded. The stop dates and reason for stopping all medications and therapies prohibited in the study will be recorded.

- Intervention
  - At least two patches; each measuring 2 cm2 and at least 1 cm from one another will be identified, mapped out, and photographed.
  - Only one of the alopecic patches will be treated.
  - The concentration of ILTA will be controlled at up to 1 mg per cubic centimeter (0.1 ml
     @ a maximum concentration of 10mg/ml) injected every 1 cm until patch has been fully treated. The researcher providing treatment will be properly trained to deliver intradermal injections using the syringe and needle-free system.
  - Med-Jet with Triamcinolone (TAC) Procedure ILTA will be administered into the patches. The PI and co-investigators will be performing interventions and follow proper training by the manufacturer on operation and handling of the device. Training will consist of a live course with a designated manufacturer technician supplemented with training videos. A standard sterile disposable 5 ml syringe will be used to draw TAC using standard sterile protocol. This syringe will be attached to the Med-Jet along with a sterile barrel and disposable sterile tip. The target lesion will be wiped with alcohol and injected with up to 10mg/ml of TAC directed towards the dermis to create a blanching wheal that is 1 cubic centimeter (total of 0.1 ml of injected fluid). The optimal injection pressure used on the subject will start at 130 pounds per square inch (psi) and increased by 5 psi until a blanching wheal is observed. The optimal pressure until the targeted patch is completely treated.
  - Patients will be treated at each visit unless complete regrowth has occurred.
     Photographs will be taken at each visit and activities will be completed as above.

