#### **Clinical Assessments**

- Physician Efficacy Assessments
  - Severity of Alopecia Tool (SALT) Score The SALT score is a visual tool to help assess percentage of hair loss on the scalp. The scalp is divided into four sections top, back, right side, and left side. Each section contributes to a total of 100% (i.e. top = 40%, back = 24%, sides = 18% each). Raters assess total percentage of hair loss in the section and then multiple is by the respective multiplier which is based on that sections total percentage of the scalp 40%, 24%, or 18%. Only terminal hairs are considered hair growth in this tool. (Olsen et al. 2004) Figure 1 illustrates the visual aid and allows for intuitive use. This is a static tool and only quantifies the hair loss at one point in time.
  - Alopecia Areata Investigator Global Assessment (AA-IGA) The AA-IGA categorizes the scalp hair loss into 5 categories based on the SALT score. The five categories are: 1 = None, 2 = Limited, 3 = Moderate, 4 = Severe, and 5 = Very Severe. The corresponding SALT scores for each category are: 1 = 0%, 2 = 1-20%, 3 = 21-49%, 4 = 50-94%, and 5 = > 95%. This is a static tool and only quantifies the hair loss at one point in time (Olsen 2004).
  - "Rule of Thumb" Assessment and Regrowth Categorization A patient's thumbprint projection is approximately 1% of the scalp surface area (King 2019). When selecting the alopecic patch for treatment and its comparator, thumb projections will be used to quantify the percentage of total scalp hair loss contributed by each these patches at baseline. At each subsequent visit, the thumbprint projection from baseline will be used to determine percent of regrowth since baseline. Based on regrowth, the patient will be categorized into one of 6 categories: A0-5. Where A0 = no change or further loss, A1 = 1-24% regrowth, A2 = 25-49% regrowth, A3 = 50-74% regrowth, A4 = 75-99% regrowth, and A5 = 100% regrowth.
- Patient-Reported Efficacy Assessments
  - Patient-Reported Hair Loss Whole Scalp This assessment will apply to the subject's whole scalp surface area. This question will be asked at every visit. And it will include 5 numerical categories: 0 = No missing hair (0% of my scalp is missing hair; I have a full head of hair); 1 = limited area (1% to 20% of my scalp is missing hair); 2 = moderate area (21% to 49% of my scalp is missing hair); 3 = large area (50% to 94% of my scalp is missing hair); and 4 = Nearly all or all (95% to 100% of my scalp is missing hair).

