## Data Analysis Plan

Statistical analyses will be completed under the supervision of a statistician. Statistical analysis will be done by statistical software (e.g. SPSS, SAS, R, Excel; etc.) AUROC will be calculated in order to assess for accuracy. The  $\chi^2$  test may be used for comparison of dichotomous variables, and the Mann-Whitney test may be used for non-normally distributed continuous variables. The cutoff value for significance was set at p = 0.05.

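### The protocol gives each child a treated and a comparator patch, but neither the A0-A5 regrowth score nor the analysis plan says that the two will be compared

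*Combined protocol and SAP*

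**What the plan says.** The Intervention text (under Prior and Concomitant Medications and Therapies) has at least two patches mapped and photographed, "at least 1 cm from one another", and states "Only one of the alopecic patches will be treated". The Rule of Thumb paragraph in Clinical Assessments gives the other patch its role: "When selecting the alopecic patch for treatment and its comparator", thumb projections record how much of the scalp hair loss each contributes at baseline. For later visits it says only that "the thumbprint projection from baseline will be used to determine percent of regrowth since baseline", then "Based on regrowth, the patient will be categorized into one of 6 categories: A0-5". The patient-reported regrowth item asks about the whole scalp and about the patches selected at baseline, but does not say whether those patches are rated separately or together. Photographs are taken at baseline and at each follow-up visit.

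The Data Analysis Plan is one short paragraph. It says "AUROC will be calculated in order to assess for accuracy", allows a chi-square test for dichotomous variables, and says "the Mann-Whitney test may be used for non-normally distributed continuous variables". It links none of these to an efficacy endpoint, a pair of groups or a visit. Efficacy is a secondary objective, and the sample of 15 is justified by pain scores only.

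**The concern.** There is no separate control group. The Background cites an estimated 80% spontaneous recovery in limited patchy disease, with no time frame, and exclusion 7 admits children on other alopecia treatment provided that it was not started within the 4 weeks before screening. Regrowth in the treated patch or over the whole scalp therefore mixes drug effect, natural recovery and background treatment. The untreated comparator is the only concurrent control, and it shares the child, the period and the background treatment.

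That control helps only if each patch has its own follow-up score and the two scores are compared within the child. Neither step is written down. If one code per child goes into the CRF, the patch difference may later be recoverable only from photographs. If both patches are scored but handled as two independent groups, precision is lost.

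**Working it through.** **The text, step by step.** Baseline sizing is explicitly for each patch. The follow-up regrowth sentence names no patch. The category sentence names the patient. The analysis paragraph names no contrast. Each step is less specific than the one before.

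**What the ambiguity can do to one record.** Take a child with 100% regrowth in the treated patch, 0% in the comparator, and patches of equal size. Scoring the treated patch gives A5, and scoring the comparator gives A0. Pooling gives 1/(1+1) = 50%, which is A3 (50-74%). The text does not choose among the three.

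**Inputs for scale.** n = 15 is from Number of Research Participants. The cutoff of 0.05 is from the Data Analysis Plan, taken here as two-sided because sidedness is not stated. The documents give no SD, effect size or within-child correlation. Assumed: SD 35 percentage points of regrowth in each patch, a true difference of 25 points, and correlation ρ from 0 to 0.7. The plan has no efficacy figure to reproduce.

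**Precision.**
- Paired half-width = t(14) × 35 × √(2(1−ρ)) / √15, with t(14) = 2.145.
  - ρ = 0: 2.145 × 49.50 / 3.873 = 27.4
  - ρ = 0.3: 2.145 × 41.41 / 3.873 = 22.9
  - ρ = 0.5: 2.145 × 35.00 / 3.873 = 19.4
  - ρ = 0.7: 2.145 × 27.11 / 3.873 = 15.0
- Unpaired half-width = t(28) × 35 × √(2/15) = 2.048 × 35 × 0.3651 = 26.2

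**Testing.** Simulation from a bivariate normal model, 40,000 runs, exact critical values (signed-rank W ≤ 25, Mann-Whitney U ≤ 64):

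| ρ | Signed-rank power | Mann-Whitney power | Mann-Whitney type I error |
|---|---|---|---|
| 0 | 43% | 44% | 4.6% |
| 0.3 | 56% | 43% | 2.1% |
| 0.5 | 70% | 42% | 0.7% |
| 0.7 | 90% | 42% | 0.2% |

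Ignoring a positive correlation makes the test conservative, so the harm is lost power rather than false positives.

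**Bounded scale.** With regrowth clipped to 0-100% (8,000 runs per setting), signed-rank power is 51-54%, 64-68% and 82-87% at latent correlation 0.3, 0.5 and 0.7, against 41-44% for Mann-Whitney. On A0-A5 codes it is 51-54%, 64-66% and 82-84%, against 40-43%. The pattern does not depend on the unbounded model.

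**Spread between patches.** If 20% or 40% of a 25-point effect reached the comparator, the true difference would be 25 × 0.8 = 20 or 25 × 0.6 = 15 points. Paired power at ρ = 0.5 would then fall from about 70% to 52% or 32%.

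**The case against.** The strongest reply is that per-patch scoring is the natural reading. The Rule of Thumb paragraph is about two patches, sizes each of them, and reuses the baseline projection at follow-up, while SALT and AA-IGA already supply patient-level scores. This stands as a plausible reading. It is not what the category sentence says, and one phrase would settle it.

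A reader might infer that the comparator is never used. The documents do not support that: it is sized at baseline, the selected patches are patient-rated at follow-up, and photographs are scheduled. The gap lies in how regrowth is scored and analysed.

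A reader might also infer that the plan commits to a wrong test. It does not: chi-square and Mann-Whitney are optional and attached to no endpoint. The power figures above show what would be lost if Mann-Whitney were applied to the patch pairs, not what the plan has decided to do. Nor can a false-positive rate be given for an uncontrolled change-from-baseline test, because the plan names no such test and gives no 12-week background regrowth rate.

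Finally, this is a secondary objective in a pilot sized on pain, with analysis supervised by a statistician. That limits the severity. It does not remove the need to fix the scoring unit before data collection.

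**Conclusion.** The point holds as a gap in specification. The protocol builds a within-child control for its efficacy objective but does not say that regrowth is scored for each patch, and it states no treated-versus-comparator contrast. Without that contrast, regrowth cannot be separated from the spontaneous recovery the protocol cites or from permitted background treatment. How much this matters over 12 weeks cannot be calculated from the documents.

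If the patches are compared without pairing, the interval half-width is 26.2 points instead of 22.9, 19.4 or 15.0 at correlation 0.3, 0.5 or 0.7. Power for a 25-point difference is then about 42% instead of about 56%, 70% or 90%. At correlation 0 pairing gains nothing (27.4 against 26.2 points). These figures rest on the assumed SD, difference and correlations. Even the paired intervals are wide, so 15 children support estimation better than testing. The sponsor should make the change; the primary tolerability objective does not depend on it.

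One wording conflict touches this point. The Intervention text says "Only one of the alopecic patches will be treated" and also "ILTA will be administered into the patches". A reader might infer that no untreated patch remains. The later wording in that bullet is singular, and Clinical Assessments refers to a comparator, so the plural alone does not support that inference. The statements still need to be reconciled.

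**What to change.** 1. **Clinical Assessments.** Score percent regrowth and A0-A5 separately for the treated and the comparator patch at weeks 4, 8 and 12. Record the patient's selected-patch regrowth rating once per patch.
2. **Data Analysis Plan.** Name the within-child difference (treated minus comparator) in percent regrowth at week 12 as the efficacy contrast. Analyse it as paired, for example by Wilcoxon signed-rank with a Hodges-Lehmann estimate and 95% CI, mainly for estimation. Other paired methods would also serve. Say how a missing week-12 score is handled. Report SALT, AA-IGA and whole-scalp ratings descriptively.
3. **Patch allocation.** Once the two patches are selected, decide which is treated from a short random list. No selection rule is given now.
4. **Limits to state.** Scoring is unmasked, and spread between patches as close as 1 cm may dilute the contrast.
5. **Separate tidying.** Reconcile the singular and plural patch wording in the Intervention text. Align the efficacy and quality-of-life entries under Data to be Collected (tPGA, pruritus score, DLQI) with the instruments described under Clinical Assessments and Quality of Life Assessment.

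The cost is protocol wording, minor CRF changes, a short random list and, if the selected patches are now rated together, one extra patient item at each of three follow-up visits. No visit or procedure is added.

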## Background

Alopecia areata (AA) is a significant medical condition that causes emotional and psychosocial distress as well as reductions in quality of life, especially in the pediatric population [Aldhouse et al 2020; Mostaghimi 2021; Christensen et al 2017]. When limited and patchy, an estimated 80% of those affected will see spontaneous recovery; however, this disease is characterized by frequent remittances and relapses and may progress to more severe disease – alopecia totalis or alopecia universalis (Ito 2012; Barton 2021). Currently, there are no Food and Drug Administration- (FDA) approved treatments for pediatric alopecia areata, and there is a paucity of well-designed, randomized-controlled clinical trials (Meah et al 2020; Barton et al. 2021). Current recommendations, however, support the use of intralesional triamcinolone acetonide (ILTA) in adults (Meah et al 2020, Yee et al 2019), and pediatric patients (Barton et al. 2021; Fernando et al. 2020; Wang et al. 2012).

The use of ILTA in the pediatric population is often limited due to fear of injections and pain [Hordinsky 2015]. A 2002 chart review by Tan et al. demonstrated >50% improvement in 65% of pediatric patients at 12 weeks with use of ILTA, but >10% of patients dropped out of the study due to pain (Tan et al 2002). Current methods for pain mitigation include small gauge needles, cold sprays, distraction, and topical anesthetics, each with their own limitations (Want et al. 2012). Controlling pain is important as it can result in several physiological, psychological, and emotional consequences such as hypoxemia, vasovagal reaction, tachycardia, life-long needle phobia, fear of other procedures, higher levels of pain during other procedures, and possible avoidance of the healthcare system as adults (Ballard et al 2018; Birnie et al 2018). Given limited treatment options for pediatric patients with AA, ameliorating the fear and pain associated with needle-based ILTA is preferable, and the Med-Jet injector may be a device that can do just that. If well-tolerated, well-designed, randomized clinical trials may be feasible in the pediatric population.

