  - 5-Point Patient-Reported Regrowth Whole Scalp and Selected Patches At each visit after the baseline visit, the subject will be asked about their perceived amount of hair regrowth both for the whole scalp and those patches selected at baseline. The subject will be able to select one of 5 categories: 1 = Further Loss, 2 = No Change, 3 = A Little Improved (<50% regrowth), 4= A lot of improvement (50-99% regrowth), and 5= Complete Regrowth (100%).

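### The physician regrowth grade gives unchanged and worsened patches the same score (A0), so the only patch-level physician rating cannot record worsening and can distort a treated-versus-comparator contrast

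*Combined protocol and SAP*

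**What the plan says.** All of this is in the combined protocol and SAP.

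- **Patch selection and baseline (Clinical Assessments, Rule of Thumb).** Both patches are sized at baseline: "When selecting the alopecic patch for treatment and its comparator, thumb projections will be used" for this. The Intervention text says that only one of the two is treated.
- **Follow-up (same item).** "the thumbprint projection from baseline will be used to determine percent of regrowth since baseline". The text does not say that the percentage is kept, that it can be negative, or that area is measured afresh.
- **Grade (same item).** "Based on regrowth, the patient will be categorized into one of 6 categories: A0-5". The lowest levels are: "Where A0 = no change or further loss, A1 = 1-24% regrowth, A2 = 25-49% regrowth". The unit graded is the patient, although two patches are being followed.
- **Other physician measures.** "The SALT score is a visual tool to help assess percentage of hair loss on the scalp"; "The AA-IGA categorizes the scalp hair loss into 5 categories based on the SALT score". Neither is specific to a patch.
- **Patient-reported regrowth (Clinical Assessments).** This is asked for the whole scalp and for the selected patches, with levels that begin: "1 = Further Loss, 2 = No Change, 3 = A Little Improved (<50% regrowth".
- **Background.** "this disease is characterized by frequent remittances and relapses and may progress to more severe disease". The same sentence puts spontaneous recovery at an estimated 80% when disease is limited and patchy.
- **Data Analysis Plan.** It lists general tests that may be used and a 0.05 cutoff. It names no treated-versus-comparator analysis of regrowth.

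**The concern.** The untreated comparator patch is what would let this study separate a drug effect from the natural course of the disease. That works only if the rating can move in both directions. Because A0 covers both stability and loss, a treated patch that holds steady while its comparator enlarges shows no difference, and neither does a treated patch that enlarges while its comparator holds steady. These are opposite results with the same score.

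The two patch-level scales also do not line up. A worsening patch has its own level on the child's scale and none on the physician's, so the two cannot be cross-checked at the lower end, where disagreement would matter most. At stake are the patch-level efficacy result and a clear physician record of treated patches that got worse.

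**Working it through.** **Stated figure.** There is none to reproduce. The documents give no SD, effect size, worsening rate or power for regrowth. The 15 subjects are justified by pain level (Number of Research Participants).

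**Step 1: single pairs.** Let T and C be the signed percent change of the treated and comparator patch (negative = loss). The true contrast is T - C. The floored contrast is max(T,0) - max(C,0).

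| T, C | True | Floored | Grades |
|---|---|---|---|
| 0, -30 | 30 | 0 | A0, A0 |
| -30, 0 | -30 | 0 | A0, A0 |
| +50, -30 | 80 | 50 | A3, A0 |
| +50, +20 | 30 | 30 | A3, A1 |
| +50, 0 | 50 | 50 | A3, A0 |

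The floor acts only when at least one patch worsens. Within a single pair it never enlarges the absolute difference.

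**Step 2: mean contrast.** Assumptions, none from the documents: T and C normal with equal SD, within-child correlation 0.5, limited to -100 and +100, 2 million simulated pairs. Reduction = 1 - floored/true.

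| Means T / C | SD | Comparators losing hair | True | Floored | Reduction |
|---|---|---|---|---|---|
| +60 / +40 | 25 | 6% | 19.5 | 19.0 | 3% |
| +60 / +40 | 40 | 16% | 17.8 | 15.7 | 12% |
| +60 / +40 | 50 | 21% | 16.8 | 13.6 | 19% |
| +50 / +20 | 25 | 21% | 29.8 | 27.0 | 9% |
| +50 / +20 | 40 | 31% | 28.3 | 22.4 | 21% |
| +50 / 0 | 25 | 50% | 49.8 | 40.0 | 20% |
| +50 / 0 | 40 | 50% | 48.0 | 34.1 | 29% |
| +30 / 0 | 25 | 50% | 30.0 | 21.4 | 29% |
| +50 / -20 | 25 | 79% | 69.8 | 47.0 | 33% |
| +10 / -20 | 25 | 79% | 30.0 | 12.7 | 58% |
| +10 / -20 | 50 | 66% | 28.5 | 13.2 | 54% |

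The 20% row combines a large treated mean with a small SD. The other rows with half or more of comparators losing hair run from 29% to 58%.

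**Step 3: the opposite direction.** Take two children with T = +50 and -50, and C = 0 in both. The true mean is (50 - 50)/2 = 0. The floored mean is (50 + 0)/2 = 25. In a simulation with independent patches, both with mean +10 but treated SD 50 and comparator SD 10, a true difference of about 0 (-0.3) becomes 13.9. So the floor can create an apparent benefit when some treated patches worsen.

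**Step 4: power at n = 15.** Two-sided signed-rank test at 0.05. At +30/0 with SD 50, signed change gives 0.54 to 0.56 across runs and A0-A5 gives 0.44 to 0.47. Adding a separate further-loss level to A0-A5 moves power only from 0.46 to 0.47. At +25/0 the same split gives 0.87 versus 0.86 (SD 25) and 0.48 versus 0.50 (SD 40). Any recovery of power therefore comes from analysing the signed value and not from splitting A0.

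**Step 5: chance that the grade misses a worsened treated patch.** If a share p of treated patches worsens, the chance of at least one among 15 is 1 - (1 - p)^15. For p = 5%, 10% and 20% (assumed) this is 54%, 79% and 96%.

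**The case against.** The strongest reply is that little is lost in practice. The Background expects most limited patchy disease to recover and cites more than 50% improvement in 65% of children given this drug by injection. On that course few patches fall below zero, and the +60/+40 rows show a reduction of only 3% to 19%. The scenarios with large reductions assume that half or more of comparators lose hair, which the documents do not support. This stands, and it is why no single figure can be given.

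Second, a reader might infer that worsening would go unseen in the study. It would not. The patient-reported scale has its own level for loss in the selected patches, photographs are taken from baseline on, and SALT would register overall scalp loss. The gap is confined to the physician's patch grade. It is still a gap, because the patient scale is the child's perception and no rating of the photographs is described.

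Third, the Data Analysis Plan names no regrowth contrast, so no planned result is biased as the text stands. This is correct: the distortion is potential. It also means that the measure can be changed before any analysis is fixed.

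**Conclusion.** The point holds as a minor weakness in a secondary endpoint. The pooling in A0 and the lack of any other patch-level physician rating are plain in the text and need no assumption. The effect on a contrast does rest on assumptions: about 3-19% shrinkage of the mean difference if most patches regrow, and about 20-58% if half or more of comparators lose hair, with correlation 0.5 and SD 25 to 50.

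Three stronger readings are not supported. A reader might infer that the floor shrinks every treated-versus-comparator difference; pairs with no worsening lose nothing. A reader might infer that the bias always runs toward no effect; Step 3 shows that it can favour treatment. A reader might infer that splitting A0 would restore power; it barely changes it.

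**What to change.** In Clinical Assessments, require that at weeks 4, 8 and 12 the current thumb-projection area of the treated patch and of the comparator be recorded separately, including spread beyond the baseline outline. Compute by program: signed percent change = 100 x (baseline area - current area) / baseline area, with negative values meaning further loss. Name this value in the Data Analysis Plan as the measure for the within-child efficacy contrast. State how patches that merge are measured, since the inclusion criteria allow a gap of only 1 cm.

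If A0-A5 is still reported, grade each patch and not the patient, and show further loss apart from no change, as the patient scale does. Present this as description.

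Cost: protocol wording and one extra recorded area per patch per follow-up visit, that is 2 x 3 = 6 values per child and 90 for 15 children. This may be a new measurement, because the current text does not clearly say that area is re-measured after baseline. No added visit is needed.
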